4.4.2.3 Clinical Benefit Rate

Clinical benefit is defined as overall objective response (CR or PR) or no disease progression for \geq 24 weeks after randomization as determined by investigator tumor assessments using RECIST v1.1. The analysis of CBR will be performed for patients with detectable *PIK3CA*-mutant tumors with measurable disease per RECIST v1.1 at baseline and will be repeated for the group of patients with detectable *PIK3CA*-mutant tumors regardless of measurable disease at baseline. To be conservative, patients with no post-baseline tumor assessment or with post-baseline tumor assessments that have overall responses of “not evaluable” will be considered to not experience clinical benefit.

An estimate of CBR and its 95% CI will be calculated using the Blyth-Still-Casella method for each treatment arm. The CBRs in the treatment arms will be compared using the stratified Mantel-Haenszel test. The CI for the difference in CBRs between the two treatment arms will be determined using the normal approximation to the binomial distribution.

4.4.2.4 Duration of Objective Response

DOR is defined as the period measured from the date of the first occurrence of a CR or PR (whichever status is recorded first) until the first date that PD or death is documented. The analysis of DOR will only include patients with detectable *PIK3CA*-mutant tumors who achieve an objective response to study treatment among patients with measurable disease per RECIST v1.1 at baseline.

Data from patients who are lost to follow-up or without disease progression or death as of the clinical data cutoff date will be censored at the time of the last tumor assessment when the patient is known to be progression-free (i.e., an overall response other than “progressive disease” or “not evaluable”).

DOR will be estimated using the Kaplan-Meier methodology, with patients grouped according to the treatment arm assigned at randomization. Comparisons between treatment arms using stratified and unstratified log-rank test will be made for descriptive purposes. Because the determination of DOR is based on a non-randomized subset of patients, formal hypothesis testing will not be performed.

4.4.2.5 Blinded Independent Central Review-Assessed Progression-Free Survival

While the primary efficacy endpoint is investigator-assessed PFS in patients with detectable *PIK3CA*-mutant tumors, a BICR of progression will be conducted for all patients based on RECIST v1.1 as described in a separate charter.

The BICR-assessed PFS in patients with detectable *PIK3CA*-mutant tumors is not intended to provide an alternative means of definitive analysis but to show that there is no potential bias in the investigator assessment. The BICR-assessed PD date and events will be defined based on the BICR assessment only. The BICR-assessed PFS analysis will be identical to the investigator-assessed PFS analysis and will also be conducted for all randomized patients with detectable *PIK3CA*-mutant tumors, with patients grouped according to the treatment arm assigned at randomization.

The Kaplan-Meier method will be used to estimate median BICR-assessed PFS for each treatment arm. Cox proportional hazards models stratified by the three stratification factors from IxRS will be used to estimate the HR and its 95% CI.

4.4.2.6 Patient-Reported Outcomes

Patient-reported outcomes (PROs) of health-related quality of life (HRQoL), treatment-related symptoms (e.g., oral mucositis, diarrhea, skin problems), and patient functioning will be captured using the following questionnaires: the European Organisation for Research and Treatment of Cancer (EORTC) Quality of Life Questionnaire Core 30 (QLQ-C30) and the modified breast cancer module QLQ-BR23 (refer to the protocol for the questionnaires).

Completion rates, i.e., complete • 1 questions on EORTC QLQ-C30 and modified QLQ-BR23 separately, will be summarized at each time point by treatment arm for patients with detectable *PIK3CA*-mutant tumors.

The population for the below PRO analyses will be defined as all randomized patients who have completed the baseline assessment (Cycle 1, Day 1) and • 1 post-baseline assessment. “Completed” means • 50% of the constituent items from the subscales and items answered.

Summary statistics (mean, SD, median, 25th and 75th percentiles, range) of linear transformed scores (Fayers et al. 2001) will be reported for selected subscales of the EORTC QLQ-C30 and the modified QLQ-BR23 or each assessment time point. The change in the linear transformed scores from baseline (Cycle 1, Day 1) for selected subscales for each assessment time point will be summarized with the aforementioned summary statistics. Proportion of the patients with single items for oral mucositis and skin problems (items 44-47 of the modified EORTC QLQ-BR23) will be summarized for each assessment time point for each single item.

The HRQoL or global health scale (Items 29 and 30 of the EORTC QLQ-C30) will be used to assess time-to-deterioration (TTD). Deterioration of HRQoL or global health scale score is defined as a decrease of • 10 points from the baseline score (Cycle 1, Day 1) with no subsequent increase above this threshold. A 10-point change is defined as the minimally important difference (Osoba et al. 1998). Data for patients who have no definitive deterioration events will be censored at the time of the last PRO assessment prior to disease progression. The Kaplan• Meier method will be used to estimate median TTD for each treatment arm. Cox proportional hazards models stratified by the three stratification factors from IxRS will be used to estimate the HR and its 95% CI.

If more than one answer is provided to a single question at one visit, the answer provided earlier will be counted in the analysis.

Additional sensitivity analyses investigating disease and treatment-related symptoms may be conducted.

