The primary progression-free survival (PFS) analysis was conducted in January 2018. At that time, the addition of taselisib to fulvestrant showed a statistically significant improvement in investigator-assessed PFS in patients with *PIK3CA*-mutant tumors. Median PFS increased from 5.4 months in the placebo arm to 7.4 months in the taselisib arm (stratified hazard ratio=0.70, p-value=0.0037). Patients treated with taselisib (versus placebo) experienced more serious adverse events (32.0% vs 8.9%), had higher rates of Grade ≥ 3 adverse events (49.5% vs 16.4%), had more frequent adverse events leading to discontinuation of taselisib/placebo (16.8% vs 2.3%), and had a slightly increased incidence of Grade 5 adverse events (1.9% vs 0.5%). The clinical benefit of the combination of taselisib and fulvestrant was considered modest, and the overall tolerability was limited.

On the basis of the results, the Sponsor decided to simplify or limit certain protocol assessments because sufficient data have been gathered for these assessments. Therefore, the primary goals of this amendment are to simplify regular tumor assessments, reduce the timeframe of the overall survival (OS) follow-up, and limit assessments in support of exploratory analyses. Safety assessments and regular clinic visits (days that fulvestrant is administered) will remain unchanged.

Changes to the protocol, along with a rationale for each change, are summarized below:

- Sections 1.3.2, 5.1.1.1.1, and 5.1.1.1.8 were updated with new taselisib adverse drug reactions detected in the primary PFS analysis and with management guidelines for infection.
- Sections 3.1, 4.5.3, 4.5.5, and Appendix 1 were updated to indicate that, after approximately the end of August 2018, tumor assessments may be conducted per local standard of care because sufficient data have been gathered for these assessments.
- Sections 3.1, 4.5.3, 4.5.5, 4.5.6, 4.5.11, 4.6.1, Appendix 1, and Appendix 2 were updated to indicate that, after approximately the end of August 2018, the following assessment are no longer required as sufficient data have been gathered for these assessments:

Tumor assessments for patients who are discontinued from study treatment for reasons other than disease progression and tumor assessments 4–6 weeks after disease progression

All patient-reported outcome (PRO) assessments

Survival and subsequent anti-cancer therapies after study treatment discontinuation

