6.7 PATIENT-REPORTED OUTCOME ANALYSES

HRQoL data will be captured using the following questionnaires: the EORTC QLQ-C30 and the modified breast cancer module, QLQ-BR23 (see [Appendix 7](#)).

The population for analysis will be defined as all randomized patients that have completed baseline and at least one post-baseline assessment. Summary statistics (mean, SD, median, 25th and 75th percentiles, and range) of linear transformed scores will be reported for selected subscales of the EORTC QLQ-C30 questionnaire and the modified BR23 (including oral mucositis and skin problems) according to the EORTC scoring manual guidelines for each assessment time point. The mean change of the

linear transformed scores from baseline (and 95% CI using the normal approximation) will also be assessed. Line charts depicting the mean changes (and standard errors) of items and subscales over time will be provided for each treatment arm from the baseline assessment. Only patients with a baseline assessment and at least one post-treatment assessment will be included in the analyses.

The HRQoL/global health scale (Items 29 and 30 of the EORTC QLQ-C30) will assess time-to-deterioration (TTD). Deterioration of HRQoL/GHS is defined as a decrease of 10 points or more from the baseline scale score with no subsequent increase above this threshold. A 10-point change is defined as the minimally important difference (Osoba et al. 1998). Data for patients who do not achieve a 10-point decrease will be censored at the last time PRO data are available. The Kaplan–Meier approach will be used to estimate median TTD for each treatment arm. Cox proportional hazard models stratified by the three stratification factors will be used to estimate the HR and its 95% CI. Data for patients without at least one post-baseline assessment will be censored at the date of randomization. Patients who had no definitive deterioration events will be censored at the time of the last available assessment prior to disease progression. Additional analyses may be conducted.

Completion rates for each PRO measure will be summarized at each timepoint by treatment arm.

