2.3 DETERMINATION OF SAMPLE SIZE

The global study plans to enroll approximately 600 patients, including 480 patients with detectable *PIK3CA*-mutant tumors and 120 patients without detectable *PIK3CA*-mutant tumors (tumor status determined by the cobas[®] *PIK3CA* Mutation Test).

After the global enrollment closes, additional Chinese patients may continue to be recruited into the China extension cohort. A total of up to 150 patients with detectable *PIK3CA*-mutant tumors may be enrolled as part of the global study population and the China extension cohort combined (refer to the protocol for details).

The sample size of 480 patients with detectable *PIK3CA*-mutant tumors is determined on the basis of the power calculation for the PFS and the OS endpoints, whichever requires a larger sample size. In this case, the sample size is driven by OS.

Among the 480 patients with *PIK3CA*-mutant tumors, approximately 287 investigator-assessed PFS events will be required to detect a hazard ratio (HR) of 0.59 in PFS (3.1 months of improvement in median PFS) with 95% power at a two-sided significance level of 1%, assuming a median PFS of 4.5 months in the control arm ([Mauriac et al. 2009](#); [Johnston et al. 2013](#)). One interim efficacy analysis of investigator-assessed PFS will be conducted at 60% of PFS information (see [Section 4.8](#) for more details). The α -spending function is specified as Gamma ($\alpha = 16$), which allocates two-sided $\alpha = 1.7 \cdot 10^{-5}$ at the interim efficacy analysis of PFS, when 172 investigator-assessed PFS events have occurred. The minimal detectable difference for PFS HR at final PFS analysis is 0.72 (i.e., 39% improvement in median PFS from 4.5 months in the control arm compared with 6.2 months in the treatment arm), when 287 investigator-assessed PFS events have occurred.

With the aforementioned sample size of 480 patients with *PIK3CA*-mutant tumors, the OS analyses in this population will require 330 deaths to detect an HR of 0.7 with at least 80% power at a two-sided significance level of 5%. Timeline for the analyses of OS is detailed in [Section 2.4](#). OS will be tested only if both the investigator-assessed PFS and ORR have reached their respective significance levels.

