For the EORTC QLQ-C30 and the modified breast cancer module QLQ-BR23 questionnaires, if $\geq 50\%$ of the constituent items are completed, a prorated score will be computed consistent with the scoring manuals and validation papers. For subscales with $< 50\%$ of the items completed, the subscale will be considered to be missing. If the additional items of the modified breast cancer module QLQ-BR23 (including oral mucositis and skin problems) have not been completed, they will be considered missing.

For the analysis of deterioration of HRQoL or global health scale, patients who have no definitive deterioration events (i.e., a decrease of ≥ 10 points from the Cycle 1, Day 1 scale score with no subsequent increase above this threshold) will be censored at the time of the last PRO assessment prior to disease progression.

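### The no-later-recovery rule for time to deterioration pulls its hazard ratio below 1 whenever PFS is longer on taselisib, even with no quality-of-life difference

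*Combined protocol and SAP*

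**What the plan says.** SAP 4.4.2.6 defines the TTD event as a fall of at least 10 points from Cycle 1 Day 1 on items 29 and 30 of the QLQ-C30, "with no subsequent increase above this threshold". SAP 4.7 repeats the condition ("scale score with no subsequent increase above this threshold"), and protocol 6.7 has the same definition. None of the three asks for a second assessment to confirm the fall.

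Under SAP 4.4.2.6, a patient without an event "will be censored at the time of the last PRO assessment prior to disease progression". Protocol 6.7 says much the same: "Patients who had no definitive deterioration events will be censored at the time of the last available assessment prior to disease progression". But protocol 6.7 also censors patients who never fall by 10 points at their last available PRO data, with no reference to progression.

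The arms are summarised by Kaplan-Meier medians, and "Cox proportional hazards models stratified by the three stratification factors from IxRS will be used to estimate the HR and its 95% CI". TTD is outside the PFS, ORR, OS testing order in SAP 4.4.2. The one sensitivity provision in SAP 4.4.2.6 is optional and concerns symptoms.

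Questionnaires are scheduled on Day 1 of each 28-day cycle and again 4 to 6 weeks and 12 weeks after progression (protocol Appendix 1, SAP Appendix 2). The SAP does not say whether the post-progression forms can be events, or can cancel an earlier fall.

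**The concern.** Whether a fall counts is decided by what comes after it. A fall with many questionnaires still to come has many chances to be cancelled; a fall close to the end has few or none. How soon the end comes depends largely on progression, and progression differs by arm: the amendment rationale in protocol version 4 reports median PFS of 7.4 months on taselisib and 5.4 on placebo, with a hazard ratio of 0.70. Chance falls that survive the rule therefore come later on taselisib, and the Cox model reads this as slower deterioration.

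The direction matters. The same rationale reports more serious adverse events on taselisib (32.0% against 8.9%) and more discontinuation of taselisib/placebo for adverse events (16.8% against 2.3%). A bias in favour of that arm could hide a real worsening. TTD is the only PRO analysis in the SAP summarised as a hazard ratio between arms.

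**Working it through.** **1. Planning inputs.** SAP 2.3 states that "approximately 287 investigator-assessed PFS events will be required to detect a hazard ratio (HR) of 0.59 in PFS", with 95% power, two-sided 1% and a control median of 4.5 months. With 2:1 allocation, events = (2.576 + 1.645)² / [(2/9) × (ln 0.59)²] = 287.9, which agrees with 287. The implied taselisib median is 4.5/0.59 = 7.63 months. The documents state no TTD hazard ratio, event rate or score SD, so there is no TTD figure to reproduce.

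**2. Mechanism by hand.** Assume each questionnaire shows a chance fall with probability p, independently and equally in both arms. Let q be the probability that a questionnaire is the patient's last. From a given visit, the chance that every remaining form shows a fall is s = p × [q + (1 − q)s], so s = pq / [1 − p(1 − q)]. This rises with q.

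With exponential PFS, 28-day visits (0.92 months) and no data cutoff, q = 1 − exp(−0.693 × 0.92 / median):

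| Medians, months (control / taselisib) | q control | q taselisib | Ratio of s, taselisib to control (p = 0.1 to 0.4) |
|---|---|---|---|
| 5.4 / 7.4 | 0.111 | 0.083 | 0.74 to 0.76 |
| 4.5 / 7.63 | 0.132 | 0.080 | 0.61 to 0.63 |
| 5.4 / 5.4 | 0.111 | 0.111 | 1.00 |

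The value of p hardly matters. By contrast, the chance that the next form shows a *first* fall is p in both arms whatever q is, so a first-fall rule gives a ratio of 1.

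**3. Simulation of the SAP rule.** The hand model omits the data cutoff, the shared baseline score and correlation between visits. The simulation included them, with no arm difference in quality of life. From the documents: 2:1 allocation, 28-day questionnaires, accrual over 28 months, cutoff at 29 months and the medians above. Assumed, because the documents are silent: within-patient SD 10 to 20 points, between-patient SD 18, visit autocorrelation 0 to 0.8, 0 to 15% missed forms, exponential PFS. Both the observed and planning PFS effects refer to *PIK3CA*-mutant patients.

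| Role of post-progression forms | HR at 5.4 / 7.4 | HR at 4.5 / 7.63 |
|---|---|---|
| Ignored | 0.81 to 0.88 | 0.69 to 0.79 |
| Can cancel a fall | 0.90 to 0.95 | 0.83 to 0.89 |
| Can cancel and can be events | 0.78 to 0.82 | about 0.71 |

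With equal PFS the result was about 1.0. With post-progression forms ignored and no data cutoff, it was 0.78 and 0.66, near the hand model.

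**4. Alternative rules, same data.** First fall of at least 10 points: 1.00 to 1.01. Two consecutive falls dated at the second: 1.00 to 1.01. Fall confirmed at the next visit, with patients whose only fall is on the last form censored at the assessment before it: 1.00 to 1.02 in one set of runs and 0.98 to 1.04 in another. Barring single last-form falls but *keeping* the no-later-recovery condition left 0.86 to 0.92 and 0.80 to 0.85, so the look-ahead condition is the cause.

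**5. Masking.** With an assumed mean worsening of 4 points on taselisib, the first-fall rule gave an HR of 1.25 to 1.27. The SAP rule gave 1.05 to 1.08 at the observed effect and 0.96 at the planning medians.

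**The case against.** Several points on the other side stand.

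- **A reader might infer that a fall on the last questionnaire always counts.** The documents do not establish this. Only the censoring date is tied to progression; the no-later-increase condition is not. If the forms at 4 to 6 and 12 weeks can cancel a fall, the bias shrinks by roughly half. It does not vanish.
- **A reader might infer that TTD merely measures time on study.** That is too strong. With pre-progression forms only, 35% to 64% of simulated events fell on the last questionnaire, so 36% to 65% came earlier.
- **A reader might quote a single hazard ratio or an inflated error rate.** Neither follows from the documents. The size needs an assumed SD, autocorrelation and follow-up pattern, and no TTD test is planned whose error rate could be inflated.
- **The consequence is limited.** In 480 patients the standard error of the log hazard ratio is about 0.16 to 0.24, and ln 0.85 = −0.16, so the shift is about one standard error or less at the reported medians. Scores and changes by visit, symptom items and completion rates are also reported.
- **The population is not fully settled.** SAP 4.4.2.6 says "The population for the below PRO analyses will be defined as all randomized patients who have completed the baseline assessment", while SAP 4.1.1 places secondary endpoints in mutant patients. If all 600 are used, the documents report no PFS effect for the 120 without a detected mutation. The simulation also ends follow-up only at progression or cutoff.
- **Sustained deterioration is a legitimate question** and differs from first fall. Replacing it outright would change the estimand.

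**Conclusion.** The concern holds as a bias of known direction and uncertain size. Under every reading of the post-progression forms examined, a PFS advantage alone moves the TTD hazard ratio below 1. At the reported medians the range is about 0.81 to 0.88 on pre-progression forms and 0.90 to 0.95 if later forms can cancel a fall; at the planning medians it is 0.69 to 0.79 and 0.83 to 0.89. These ranges rest on the assumptions in the working and are not properties of the trial data.

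Because TTD is descriptive and outside the testing hierarchy, this does not touch the primary or key secondary conclusions. It does mean that a hazard ratio below 1 under the current definition is not, by itself, evidence of better quality of life on taselisib, and that one near 1 could hide harm.

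**What to change.** In SAP 4.4.2.6 and 4.7:

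1. State whether questionnaires after progression can be TTD events, and whether they count as subsequent scores that cancel an earlier fall. Bring protocol 6.7 into line.
2. Keep the current TTD and report two analyses beside it: time to first fall of at least 10 points, and time to a fall confirmed at the next scheduled assessment. The second must drop the no-later-increase condition and censor patients whose only fall is on the last questionnaire at the assessment before it. State which of the two assessments dates the event.
3. State that a hazard ratio below 1 from the current definition will not be interpreted as a quality-of-life benefit unless these two analyses agree.

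The cost is some SAP text and two re-derivations from data already collected. First-fall TTD counts transient falls, so its medians will be shorter. If the analyses are added after unblinding, they must be labelled post hoc.

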3.3.7 Rationale for Patient-Reported Outcome Assessments

MBC is not currently considered curable; therefore, a patient's HRQoL is an important multi-dimensional construct to measure because impairment of function and experience of treatment-related symptoms affect patient outcomes (Beslija et al. 2009; Irwin et al. 2011). Elucidating treatment effect on HRQoL, specifically during PFS,

provides supportive evidence to the benefit-risk assessment of a medicine and informs the treatment decision-making between patient and clinician.

PRO measures will contextualize a patient's experiences in the study. Since treatment-related side effects (e.g., oral mucositis, diarrhea, and skin problems) have the potential to affect HRQoL, it is crucial to characterize not only the incidence of these side effects but also the impact from the patient's perspective. Assessment of global quality of life, impairment of function, and symptoms of special interest will provide a more comprehensive understanding of treatment impact and tolerability.

The EORTC QLQ-C30 and QLQ-BR23 demonstrate strong psychometric properties, of both reliability and validity, and capture important constructs of interest. The QLQ-BR23 will be modified to include validated items on oral mucositis (2 items) and skin problems (2 items) to characterize these symptoms of special interest.

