4.5.11 Follow-Up Assessments

Until approximately the end of August 2018, patients who are discontinued from study treatment for reasons other than disease progression will be asked to continue to have tumor assessments performed and complete the PRO assessments approximately every 8 weeks (± 5 days) until disease progression.

Until approximately the end of August 2018, after study treatment discontinuation, patients will be followed for survival and subsequent anti-cancer therapies approximately every 3 months until death, loss to follow-up, withdrawal of consent, or study termination by the Sponsor.

Until approximately the end of August 2018, after experiencing disease progression, patients will also be asked to return to the clinic 4–6 weeks (for tumor and PRO assessments) and 12 weeks ± 7 days (for PRO assessments), even if a patient initiates anti-cancer therapy subsequent to study drug discontinuation.

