Appendix 1 Schedule of Assessments (cont.)

- r Archival tumor tissue blocks or a minimum of 20 (25 preferred) freshly cut unstained slides from the most recent tumor tissue will be collected at screening for molecular characterization of the tumor tissue including but not limited to PIK3CA mutation. If a tissue sample from the site(s) of metastasis was collected to meet enrollment criteria, a minimum of five additional formalin-fixed paraffin-embedded tissue slides of the primary lesion should be provided, if available.
- s Tumor biopsy collection at the time of disease progression is not required for study participation but, *until approximately the end of August 2018*, is strongly recommended and will be collected for patients who sign the Optional Research Informed Consent Form.
- t *Until approximately the end of August 2018*, the PRO questionnaires (EORTC QLQ-C30, modified QLQ-BR23) and EQ-5D will be completed by the patients at the investigational site during treatment. All questionnaires must be administered prior to any other study assessment(s), health care provider interaction, and administration of study drug, to ensure that the validity of the instrument is not compromised and that data quality meets regulatory requirements. *Until approximately the end of August 2018*, patients who are discontinued from study treatment for reasons other than disease progression will be asked to continue to complete the PRO assessments approximately every 8 weeks (± 5 days) until disease progression. Additionally, *until approximately the end of August 2018*, all patients will also complete the PRO measures once at 4–6 weeks (± 5 days) and once at 12 weeks (± 7 days) after disease progression.
- u Fulvestrant will be administered in the clinic (before administration of taselisib/placebo) as two intramuscular injections of 250 mg each on Days 1 and 15 of Cycle 1 and Day 1 of each subsequent 28-day cycle.

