Table 2	Interim Analyses for Overall Survival if the First Interim Overall Survival Analysis Occurs at the Time of the Interim Efficacy Analysis of Investigator-Assessed Progression-Free Survival	13
Table 3	Interim Analyses for Overall Survival if the First Interim Overall Survival Analysis Occurs at the Time of the Final Efficacy Analysis of Investigator-Assessed Progression-Free Survival	14

LIST OF APPENDICES

Appendix 1	Protocol Synopsis	23
Appendix 2	Schedule of Assessments.....	33

1. **BACKGROUND**

Study GO29058 is a Phase III, double-blind, multicenter, randomized, placebo-controlled study designed to evaluate the efficacy and safety of taselisib + fulvestrant compared with placebo + fulvestrant in postmenopausal women with estrogen receptor-positive and human epidermal growth factor 2 (HER2)-negative locally advanced or metastatic breast cancer (MBC) who have disease recurrence or disease progression during or after aromatase inhibitor therapy.

Approximately 600 patients will be enrolled in the global study, including 480 patients with detectable *PIK3CA*-mutant tumors and 120 patients without detectable *PIK3CA*-mutant tumors. Patients will be randomized in a 2:1 ratio to receive either fulvestrant + taselisib or fulvestrant + placebo. Patients with and without detectable *PIK3CA*-mutant tumors will be randomized separately.

The primary efficacy endpoint is investigator-assessed progression-free survival (PFS) in patients with detectable *PIK3CA*-mutant tumors, and the secondary efficacy endpoints are overall objective response rate (ORR), overall survival (OS), clinical benefit rate (CBR), duration of objective response (DOR), and blinded independent central review (BICR)-assessed PFS in patients with detectable *PIK3CA*-mutant tumors. The safety of taselisib and fulvestrant compared with placebo and fulvestrant will be evaluated in patients with detectable *PIK3CA*-mutant tumors and also in all randomized patients who receive at least one dose of any component of protocol treatment (i.e., study drug).

The purpose of this Statistical Analysis Plan (SAP) is to provide the analysis plan proposed for this study by the Sponsor, F. Hoffmann-La Roche Ltd. The SAP overrides the analyses described in the statistical section of the protocol. The analyses as described in the SAP will be used by the Sponsor for the purpose of regulatory submission.

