- ^t The PRO questionnaires (EORTC QLQ-C30, modified QLQ-BR23) and EQ-5D will be completed by the patients at the investigational site during treatment. All questionnaires must be administered prior to any other study assessment(s), health care provider interaction, and administration of study drug, to ensure that the validity of the instrument is not compromised and that data quality meets regulatory requirements. Patients who are discontinued from study treatment for reasons other than disease progression will be asked to continue to complete the PRO assessments approximately every 8 weeks (± 5 days) until disease progression. Additionally, all patients will also complete the PRO measures once at 4•6 weeks (± 5 days) and once at 12 weeks (± 7 days) after disease progression.
- ^u Fulvestrant will be administered in the clinic (before administration of taselisib/placebo) as two intramuscular injections of 250 mg each on Days 1 and 15 of Cycle 1 and Day 1 of each subsequent 28-day cycle.

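### Time to deterioration: as written, events may fall after progression but event-free patients are censored before it, which tilts the HR toward the arm with longer PFS

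*Combined protocol and SAP*

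**What the plan says.** SAP 4.4.2.6 counts a TTD event when the global health score falls at least 10 points from Cycle 1 Day 1 and does not later recover above that threshold. It does not say that the fall must occur before progression. The censoring rule does refer to progression: "Data for patients who have no definitive deterioration events will be censored at the time of the last PRO assessment prior to disease progression". SAP 4.7 repeats the pair, describing patients without a fall "with no subsequent increase above this threshold) will be censored at the time of the last PRO assessment prior to disease progression". The HR comes from a stratified Cox model.

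Questionnaires continue past progression. SAP Appendix 2, footnote t: "Additionally, all patients will also complete the PRO measures once at" 4–6 weeks and once at 12 weeks after progression. Protocol Appendix 1, footnote t, has the same schedule ("all patients will also complete the PRO measures once at" those times), limited to the period up to about the end of August 2018. Protocol 4.5.11 asks for these visits "even if a patient initiates anti-cancer therapy subsequent to study drug discontinuation".

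Protocol 6.7 carries two censoring rules, one at the last available questionnaire and one at the last before progression. The SAP keeps only the second, and SAP Section 1 settles which governs: "The SAP overrides the analyses described in the statistical section of the protocol". Protocol 3.3.7 gives the purpose: "Elucidating treatment effect on HRQoL, specifically during PFS".

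**The concern.** Take two patients who progress at month 5, both stable until then. One first deteriorates at the 12-week post-progression questionnaire and is an event at about month 7.8. The other is still stable at that questionnaire and is censored back at about month 5. Among patients progressing at that time, the follow-up counted after progression belongs only to those who go on to have the event.

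That alone would raise the apparent deterioration rate in both arms. It becomes a between-arm distortion when PFS differs, because the arm that progresses sooner enters this event-only stretch more often. The trial assumed longer PFS on taselisib and observed it, so the tilt favours taselisib. TTD is the only between-arm PRO comparison that SAP 4.4.2.6 models, and it bears on benefit-risk in a trial whose own amendment calls the benefit modest and tolerability limited.

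**Working it through.** The plan gives no power, event count or expected HR for TTD, so there is no TTD figure to reproduce. The check asks what the written rule returns when treatment has no effect on deterioration.

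**Inputs from the documents.** PFS medians 5.4 (placebo) and 7.4 months (taselisib), from the protocol amendment rationale; 2:1 allocation; scans every 8 weeks; 28-day cycles; post-progression questionnaires at 4–6 weeks (taken as 5) and 12 weeks; PFS cutoff about 29 months after first patient in.

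**Assumed, because the documents do not give them.** Deterioration median 3 to 24 months; post-progression completion 10% to 100%; deterioration hazard after progression unchanged or doubled; the PIK3CA-mutant PFS medians applied to all patients.

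**Hand check (continuous time, no cutoff).** Let λ be the deterioration rate, μ the progression rate and w = 84/30.44 = 2.76 months. The chance of deteriorating within the post-progression window is q = 1 − exp(−λw). The event-only time it adds per progressor is E = q/λ − w·exp(−λw). The event rate under the written rule is (λ + μq)/(1 + μE).

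With a deterioration median of 15 months, λ = 0.693/15 = 0.0462, q = 0.120 and E = 0.162.
- Placebo: μ = 0.693/5.4 = 0.1284; rate = (0.0462 + 0.0154)/1.0208 = 0.0603
- Taselisib: μ = 0.693/7.4 = 0.0937; rate = (0.0462 + 0.0112)/1.0152 = 0.0566
- Ratio: 0.0566/0.0603 = 0.94, although the true ratio is 1

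If events also stop at progression, both rates equal λ and the ratio is 1. If μ is equal in the two arms, the ratio is 1 under the written rule as well.

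**Simulation.** 1,000,000 patients per scenario on the actual visit grid, unstratified Cox, true HR 1. Each cell is the fall in HR from the matched rule (events and censoring both stop at progression) to the written rule. It spans the deterioration medians and both readings of prior to progression (progression-visit questionnaire counted or not).

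| Post-progression completion | Hazard unchanged | Hazard doubled |
|---|---|---|
| 100% | 0.02–0.09 | 0.03–0.12 |
| 75% | 0.02–0.08 | 0.02–0.11 |
| 50% | 0.02–0.07 | 0.02–0.10 |
| 25% | 0.01–0.05 | 0.01–0.08 |
| 10% | 0.00–0.04 | 0.00–0.06 |

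In HR terms, with completion of 60–100% and the hazard unchanged, the written rule gives 0.91–0.96 and matched windows 0.99–1.01. With equal PFS in both arms every rule gives 0.99–1.01. At full completion with unchanged hazard, about 12–18% of events fall after progression.

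**Shared prognosis.** If the same patients tend both to progress and to deteriorate early (gamma frailty, variance 0.5), the written rule gives 0.97–0.99, the matched pre-progression window 1.03–1.05 and the matched all-questionnaire window 1.01–1.03. The gap between written and matched pre-progression rules remains, at about 0.04–0.09.

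**Scale.** With 600 patients and deterioration medians of 9–24 months, the standard error of the log HR is about 0.13–0.20. With 480 it is larger by √(600/480) = 1.12.

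**The case against.** The strongest reply is intent. Protocol 3.3.7 speaks of quality of life during PFS, and of the protocol's two censoring rules the SAP kept the one tied to progression. A programmer who took that as the analysis window would have stopped events there too, and nothing would be wrong. This stands as a possibility. It does not remove the gap: 3.3.7 is a rationale and not an event rule, no passage excludes later falls, and two people following the SAP faithfully could report different HRs.

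The second reply is that matching does not make the estimate unbiased. That is correct. Under shared prognosis the written rule lies at least as near 1 as the matched pre-progression rule, because two biases partly cancel. That cancellation is accidental and cannot be relied on, but the fix should not be presented as more than it is.

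The third is size and population. The PFS medians are for PIK3CA-mutant patients, while SAP 4.4.2.6 defines the PRO population as all randomized patients with a baseline and a later questionnaire. SAP 4.1.1 places secondary analyses in mutant patients, so the intended population is unclear. If 120 of 600 patients (20%) had equal PFS in both arms, one such run gave a gap of about 0.04 (0.96 against 1.00). This stands, and it is one more reason to give the size as an assumption-driven range.

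**Conclusion.** The rule as written has mismatched windows, and its direction is predictable: toward the longer-PFS arm. At the observed medians the shift is roughly 0 to 0.12 in HR: about 0.02–0.09 with moderate to full post-progression completion and unchanged hazard, near 0 with very low completion, and about 0.12 if the hazard doubles at progression. It is worth correcting because it is directional and cheap to remove, not because it is large.

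Four stronger inferences are tempting and not supported.
- That the range is a bound. It is not: tripling the hazard gave 0.85 against 0.97 in one scenario, a shift of about 0.13, and the documents fix none of these inputs.
- That the reported TTD result is biased. The documents contain neither the derivation used nor a TTD result.
- That the trial's error control is affected. Only PFS, ORR and OS are in the testing hierarchy; TTD has no significance level, and the shift is below one standard error.
- That the endpoint should be replaced, for example by a fall confirmed at the next questionnaire. That is a different estimand which the documents do not call for. Under shared prognosis without noise it gave 1.05–1.07, further from 1 than the written rule.

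**What to change.** In SAP 4.4.2.6 and 4.7, state one window for all three elements: when an event can occur, which later scores can cancel it, and where patients without an event are censored. Use questionnaires on or before the progression date as the stated rule, in line with the aim in protocol 3.3.7, and say explicitly that the progression-visit questionnaire counts. Report the all-questionnaire window as a sensitivity analysis, with events, recovery and censoring all running to the last available questionnaire. The sensitivity version answers a broader question: if deterioration speeds up after progression, its HR also reflects the PFS difference (about 0.95 when the hazard doubles).

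Add one sentence saying that matching removes only the window artefact. Censoring at progression may still be informative, and matched HRs can lie slightly above 1 when prognosis for progression and deterioration is shared.

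"The primary progression-free survival (PFS) analysis was conducted in January 2018", so any rerun is post hoc. Label it so and show it beside the result from the rule actually used. If events were already limited to the period up to progression, stating that is enough for the main result.

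Cost: a few sentences in two SAP sections and two reruns of one Cox model on existing data. No new data are needed.
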